4.11.3.3. Glycemic Variability

Glycemic variability will be evaluated using the notation below:

i represents a time point within a time period (a 24-hour period, daytime or nighttime)

n represents the number of time points within the time period

k represents a day within a visit

m represents number of days CGM is performed at a visit

$BG_{k,i}$ represents the glucose value at time point i on day k unless otherwise specified.

- Within-Day Variability

For variables assessing within-day variability, first determine the variability within each day, then average across days within a visit.

Within-day glucose SD (Rodbard 2009):

$$SD = \frac{1}{m} \sum_{k=1}^m SD_k = \frac{1}{m} \sum_{k=1}^m \sqrt{\frac{\sum_{i=1}^n (BG_{k,i} - \frac{\sum_{i=1}^n BG_{k,i}}{n})^2}{n-1}}$$

Within-day glucose CV (Clarke and Kovatchev 2009):

$$CV = \frac{1}{m} \sum_{k=1}^m CV_k = \frac{1}{m} \sum_{k=1}^m \frac{SD_k}{\left(\frac{\sum_{i=1}^n BG_{k,i}}{n}\right)} \times 100$$

Inter-quartile range (IQR) (Mazze et al. 2008):

$$IQR = \frac{1}{m} \sum_{k=1}^m IQR_k = \frac{1}{m} \sum_{k=1}^m (75\text{th} - 25\text{th percentile of all BG values on day } k)$$

- Between-Day Variability

For variables assessing between-day variability, first determine the variability for each time point across days within a visit then average across all time points.

Between-day glucose SD (Rodbard 2009):

$$SD = \frac{1}{n} \sum_{i=1}^n SD_i = \frac{1}{n} \sum_{i=1}^n \sqrt{\frac{\sum_{k=1}^m (BG_{k,i} - \frac{\sum_{k=1}^m BG_{k,i}}{m})^2}{m-1}}$$

Between-day glucose CV (Kovatchev et al. 2009):

$$CV = \frac{1}{n} \sum_{i=1}^n CV_i = \frac{1}{n} \sum_{i=1}^n \frac{SD_i}{\left(\frac{\sum_{k=1}^m BG_{k,i}}{m}\right)} \times 100$$

Mean of daily differences (MODD): this parameter is calculated as the mean of absolute differences between glucose values at corresponding time points of consecutive days.

$$\text{MODD} = \frac{1}{m-1} \sum_{k=1}^{m-1} \frac{\sum_{i=1}^n |BG_{k+1,i} - BG_{k,i}|}{n}$$

- Overall Variability

The CV, SD, IQR, LBGi, HBGI, and BGRI will be calculated using the standard formulas.

- Risk for Hypo/Hyperglycemia

The LBGi has been developed to quantitate both frequency and severity of hypoglycemia. The LBGi has been validated as a predictor of severe hypoglycemia, which is an SAE and could result in coma or death if unrecognized and untreated. The HBGI quantifies both frequency and severity of hyperglycemia and has been related to HbA1c and risk for hyperglycemia (Kovatchev et al. 2006). Additionally, both the LBGi and HBGI have a high sensitivity to changes in glycemic profiles and control (Kovatchev et al. 2006). The LBGi is a non-negative number that increases as the number of low readings increases. The HBGI is a non-negative number that increases as the number of high readings increases.

The LBGi, HBGI, and blood glucose risk index (BGRI) will be derived for each day of a visit and for overall in the following steps:

Step 1: For each blood glucose (BG [mg/dL]) at the i^{th} time point, compute the following:

$$f(\text{BG}_i) = 1.509 \times [(\ln(\text{BG}_i))^{1.084} - 5.381]$$

This transforms the BG data using a nonlinear transformation that maps the BG range of 20 to 600 mg/dL to a symmetric interval of $(-\sqrt{10}, \sqrt{10})$

The center of the BG scale is 112.5 mg/dL and is mapped to 0

Step 2: Compute BG risk for each reading

$$\text{rl}(\text{BG}_i) = 10 \times f(\text{BG}_i)^2 \text{ if } f(\text{BG}) < 0; \text{ otherwise } \text{rl}(\text{BG}_i) = 0$$

$$\text{rh}(\text{BG}_i) = 10 \times f(\text{BG}_i)^2 \text{ if } f(\text{BG}) > 0; \text{ otherwise } \text{rh}(\text{BG}_i) = 0$$

Assign the risk of each BG value by applying the above quadratic risk function

Value range from 0 (achieved when BG = 112.5, the center) to 100

Left side of the parabola is risk of hypoglycemia, and the right side is risk of hyperglycemia

Step 3: Compute LBGI and HBGI

$$\text{LBGI} = \frac{1}{n} \sum_{i=1}^n \text{rl}(\text{BG}_i)$$

$$\text{HBGI} = \frac{1}{n} \sum_{i=1}^n \text{rh}(\text{BG}_i)$$

Step 4: Compute BGRI

$$\text{BGRI} = \text{LBGI} + \text{HBGI}$$

4.12. Subgroup Analyses

The subgroups will be defined as:

- Body mass index (<30, ≥30)
- Baseline HbA1c (<8.5% and ≥8.5%)

The outcome measures included in the subgroup analyses are:

- HbA1c and change in HbA1c from baseline to up to 32 weeks
- Documented hypoglycemia and nocturnal hypoglycemia rates (<54 mg/dL [3.0 mmol/L]) during 0-32 weeks.

Analyses for HbA1c and its change will be performed examining the 3-way interaction of the primary treatment arms, visit and the subgroup variable using the same MMRM model described for the primary analysis. This model will include the same fixed effects given for the primary analysis model plus factors of subgroup, 2-way interaction of subgroup and treatment, 2-way interaction of subgroup and visit, and 3-way interaction of treatment, visit, and the subgroup.

The hypoglycemia rates will be analyzed using a negative binomial regression including the same fixed effects for hypoglycemia event analyses plus factors of subgroup, 2-way interaction of subgroup and treatment.

The interaction effects will be evaluated using a significance level of 0.1, unadjusted. If the interaction effect is significant ($p < 0.1$), separate analysis without the terms related with the subgroup will be performed for each subpopulation.

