#### **10.3.7.2. Subgroup Analyses**

Subgroup analyses of important factors, including age, race, ethnicity, gender, duration of diabetes, baseline HbA1c ( $<8.5\%$ ,  $\geq 8.5\%$ ), BMI, and other factors to be specified in the SAP are planned for the key outcomes of HbA1c, insulin dose and incidence and rate of hypoglycemia.

These will be conducted using the analysis of covariance model with strata, treatment, factor, treatment-by-factor interaction as fixed effects, and baseline as covariate.

Covariate analysis of PK and PK/PD may be performed.

Other exploratory subgroup analyses may be performed as deemed appropriate.

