4.1. General Considerations

All data will be entered, verified, and archived at a contract research organization (CRO) external to Eli Lilly and Company (Lilly) and/or at Lilly. Data listings, summaries, and analyses will be performed by a CRO and/or by Lilly under the guidance and approval of statisticians at Lilly.

Statistical analysis of this study will be the responsibility of Lilly. Any change to the data analysis methods described in the protocol will require an amendment ONLY if it changes a principal feature of the protocol. Any other change to the data analysis methods described in the protocol, and the justification for making the change, will be described in this SAP and/or in the clinical study report (CSR). Additional exploratory analyses will be conducted, as deemed appropriate.

Unless otherwise specified, listings will be ordered by the patient ID nested within the investigator site.

The patient populations used for this study are described below:

Population and Analysis Set	Description
Entered/Enrolled Population	All study participants who sign informed consent
Randomized Population	All study participants who are randomly assigned a treatment arm
Efficacy analysis set (EAS)	Data for all randomized study participants who receive at least one dose of study medication, excluding data after using rescue medication(not acute therapy) or stopping study medication (last dose date + 10 days). In the event of a treatment error, participants will be analyzed according to the treatment they actually received.
Safety Population	All randomized study participants who receive at least one dose of study medication.
CGM Population	All randomized study participants who receive at least 1 dose of study medication, and have CGM data from at least 1 collection period.

Abbreviations: CGM = continuous glucose monitoring.

Safety analyses will be conducted using the Safety Population with all data collected during the study including treatment and follow-up period regardless of the treatment disposition status. Efficacy analyses will be conducted on the efficacy analysis set (EAS), unless otherwise specified.

Unless otherwise noted, all tests of treatment effects will be conducted at a 2-sided alpha level of 0.10 and confidence intervals (CIs) will be calculated at 90%, 2-sided. All tests of interactions between treatment groups and other factors will be conducted at a 2-sided alpha level of 0.10.

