4.7. Primary Outcome and Methodology

The primary efficacy measure of change in HbA1c at Week 32 (together with HbA1c measure at other postbaseline visits) will be summarized and analyzed using an MMRM approach on the EAS. This model implicitly adjusts for missing data through a variance-covariance structure. This model will include the fixed effects of treatment (LY3209590 Algorithm 1, LY3209590 Algorithm 2, insulin degludec), stratification factors (country, BMI strata [BMI <30 or ≥30], sulfonylureas use[Y/N]), visit, treatment by visit interaction, and baseline value of the dependent variable as the fixed effects. The HbA1c is reported in unit of % and will be converted to the unit of mmol/mol using the following formula: HbA1c in mmol/mol = 10.93*HbA1c in % - 23.5 (<http://www.ngsp.org/ifccngsp.asp>). HbA1c analysis will be conducted based on both units.

In the MMRM model, the within-patient errors are modeled as an unstructured variance-covariance matrix. If the analysis fails to converge, the following variance-covariance matrix will be used (in order) until one converges:

1. toeplitz with heterogeneity
2. autoregressive with heterogeneity
3. compound symmetry with heterogeneous variances
4. toeplitz
5. autoregressive
6. compound symmetry without heterogeneous variances

The Kenward-Roger approximation will be used to estimate denominator degrees of freedom for the MMRM models. The following is an example SAS code:

```
proc mixed data=DATA;
  class TREATMENT STRATIFICATIONS VISIT PATIENT;
  model HbA1c=BASELINE TREATMENT STRATIFICATIONS VISIT
        VISIT*TREATMENT / solution ddfm=kr;
  repeated VISIT / subject=PATIENT type=un;
  lsmeans TREATMENT*VISIT/ pdiff cl alpha=0.1 om=DATA;
run;
```

The 2-sided 90% CI for the LS mean for the individual treatment arms, treatment LS mean difference (LY3209590 Algorithm 1 vs. insulin degludec, LY3209590 Algorithm 2 vs insulin degludec, and LY3209590 Algorithm 1 vs LY3209590 Algorithm 2) in the change in HbA1c at 32 weeks will be constructed. Similar summary will be provided for the comparison between pooled LY arm and insulin degludec based on the contrast from the above MMRM model.

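### The HbA1c subgroup test named in SAP 4.12 asks whether a subgroup difference changes across visits, not whether there is one at Week 32

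*SAP*

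**What the plan says.** SAP section 4.12 defines two subgroup factors, BMI (<30, ≥30) and baseline HbA1c (<8.5%, ≥8.5%). For HbA1c it says: "Analyses for HbA1c and its change will be performed examining the 3-way interaction of the primary treatment arms, visit and the subgroup variable". The model is the primary MMRM plus subgroup, subgroup by treatment, and the "2-way interaction of subgroup and visit, and 3-way interaction of treatment, visit, and the subgroup".

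The decision rule follows: "The interaction effects will be evaluated using a significance level of 0.1, unadjusted". If the interaction effect reaches p<0.1, "separate analysis without the terms related with the subgroup will be performed for each subpopulation". Section 4.1 sets the same level for the whole plan: "All tests of interactions between treatment groups and other factors will be conducted at a 2-sided alpha level of 0.10".

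Three other places bear on this:

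- SAP 4.7 analyses Week 32 HbA1c "together with HbA1c measure at other postbaseline visits", and "the within-patient errors are modeled as an unstructured variance-covariance matrix".
- For hypoglycemia rates, SAP 4.12 adds only the 2-way subgroup-by-treatment term.
- Protocol 10.3.7.2 plans an "analysis of covariance model with strata, treatment, factor, treatment-by-factor interaction as fixed effects, and baseline as covariate", with no visit term.

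Neither document specifies a treatment-by-subgroup contrast at Week 32.

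**The concern.** The primary endpoint is HbA1c change at Week 32, so the natural subgroup question is whether the LY-versus-degludec difference at Week 32 depends on BMI or baseline HbA1c. Once the 2-way terms are in the model, the 3-way term does not answer that. It compares the treatment-by-subgroup difference at one visit with the same difference at other visits, so whatever is common to all visits cancels.

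This has two consequences. A stable subgroup difference can be missed however large it is. A difference seen only early can set off separate subgroup analyses when nothing remains at Week 32. Both factors also stratify the randomisation (Protocol 7.2), and the result of a Phase 2 subgroup screen may be carried into later designs.

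**Working it through.** **The plan's own figure.** Protocol 10.1 states 90% power for pooled LY (200) versus degludec (100), margin 0.4%, SD 1.1%, true difference 0, two-sided alpha 0.1. SE = 1.1 × √(1/200 + 1/100) = 0.1347; 0.4/0.1347 = 2.969; Φ(2.969 − 1.645) = 0.907. The 90% reproduces. No power is stated for any subgroup test.

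**Inputs from the documents.** 100 completers per arm, SD 1.1%, alpha 0.10, three arms, two levels per subgroup factor.

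**Assumed inputs.**
- Five post-baseline HbA1c visits (Weeks 6, 12, 18, 28, 32), read from a broken schedule table.
- Subgroup splits from 50/50 to 70/30.
- An interaction of 0.6% HbA1c, the same in both LY arms.
- Visit correlation of either AR 0.75 per 10 weeks or exchangeable 0.7.
- Complete data.

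**Algebra.** Let δ_v be the subgroup difference in the LY-minus-degludec effect at visit v. The 3-way test, with (3−1)(2−1)(5−1) = 8 df, has noncentrality that depends only on differences between the δ_v. If all δ_v are equal it is exactly zero, and the rejection rate is alpha whatever the size of δ. No assumed figure enters this step.

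**Week 32 contrast.** Let f = 1/(100s) + 1/(100(1−s)) for subgroup share s. With the same δ in both LY arms, the noncentrality is λ = δ² / (1.5 × f × SD²), for both the 2-df and the pooled 1-df test.
- 50/50: f = 0.04; 1.5 × 0.04 × 1.21 = 0.0726; λ = 0.36/0.0726 = 4.96. Power is 63% (2 df) and 72% (1 df).
- 70/30: f = 0.0476; 1.5 × 0.0476 × 1.21 = 0.0864; λ = 4.17. Power is 56% and 65%.

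**3-way and visit-averaged 2-way tests, exchangeable correlation ρ = 0.7, 50/50 split.**
- 3-way: λ = Σ(δ_v − mean)² / (0.0726 × 0.3).
  - 0.3% at Week 6, then 0.6%: mean 0.54, sum of squares 0.24² + 4 × 0.06² = 0.072, λ = 3.31, power 31%.
  - 0.6% to Week 18, then zero: mean 0.36, sum of squares 3 × 0.24² + 2 × 0.36² = 0.432, λ = 19.8, rejection 95%.
- 2-way (2 df): λ = mean² / (0.0726 × (0.7 + 0.3/5)).
  - Constant 0.6%: 0.36/0.0552 = 6.52, power about 74%.
  - Transient: 0.36²/0.0552 = 2.35, rejection 37%.

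Over both splits and both correlation structures:

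| Profile of the 0.6% difference | 3-way (8 df) | Week 32, 2 df | Week 32 pooled, 1 df | Visit-averaged 2-way |
|---|---|---|---|---|
| Equal at all visits | 10% | 56–63% | 65–72% | 67–74% |
| 0.3% at Week 6, then 0.6% | 27–35% | 56–63% | 65–72% | not needed here |
| 0.6% to Week 18, then zero | 64–95% | 10% (no difference at Week 32) | 10% | 33–38% |

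**Check by simulation.** With 4,000 complete-data trials per scenario (unstructured covariance, five visits, correlation 0.6), the 3-way test rejected in 9.9% at a constant 0.6% and 10.5% at a constant 1.0%.

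**Sensitivity for a building difference.** For one reaching 40%, 75%, 90%, 100% and 100% of its final size, 3-way power was 15–57% over final sizes of 0.4–0.8%, smaller-subgroup shares of 30–50%, four or five visits and three correlation structures. At 0.6%, a 50/50 split and five visits it was 24–36%, against 63% for the Week 32 contrast.

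**The case against.** **Presence is not equal size.** A reader might infer that any subgroup difference present at every visit has only alpha-level power. The documents do not support that. Alpha-level power needs equal size at all visits, and the protocol points to effects that build: section 5.4 ties the 32-week duration to slow escalation, and 5.5 puts steady-state glucose at 4 to 10 weeks. A growing difference gets more than 10%, though usually well below the Week 32 contrast. This limits the claim but does not remove it.

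**The trigger is not explicit.** A reader might also infer that the 3-way term is the sole trigger. It is the only term the HbA1c sentence names, so this is the natural reading. But the rule speaks of interaction effects in the plural, and the same paragraph serves the hypoglycemia model, which has only the 2-way term. If the 2-way term counts, a constant difference is detectable (67–74%), slightly better than with the 2-df Week 32 contrast. That stands. The 2-way term still averages over visits, however, and fires in 33–38% of trials when nothing is left at Week 32.

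**The rule does not suppress estimates.** It governs only the separate refits. The interaction model is run regardless, and SAP 4.1 has LS means displayed by treatment and visit for MMRM analyses. It does not expressly promise them by subgroup.

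**Departing from the protocol is not in itself an error.** Both documents allow non-principal changes, with the justification in the SAP or study report. SAP 4.12 also covers HbA1c change up to 32 weeks, so examining the trajectory is legitimate as an addition.

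**Size.** An interaction of 0.6% exceeds the 0.4% margin. At 0.4%, even the 2-df Week 32 contrast has only 32–36% power, which is a reason to rely on estimates and intervals rather than on any test.

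**Conclusion.** The point holds in limited form. As written, the one interaction that SAP 4.12 names for HbA1c tests change over visits. It has no power beyond alpha for a difference of equal size throughout, reduced power for one that builds (27–35% in the two-step illustration), and a high rejection rate (64–95%) for one that has vanished by Week 28. The first statement is algebra. The other figures depend on the assumed interaction size, time profile, visit count, subgroup split and correlation, with the protocol SD of 1.1% and 100 completers per arm.

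Whether the 3-way term alone opens the separate analyses is the natural but not the certain reading. Under either reading, no stated test addresses Week 32. The consequence is confined to subgroup interpretation; the primary analysis is untouched. The section should be corrected, but this does not threaten the trial's main result.

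**What to change.** Keep the MMRM with all its subgroup terms. In SAP 4.12:

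- Name the treatment-by-subgroup contrast at Week 32 as the HbA1c interaction test: pooled LY versus degludec (1 df), and each LY arm versus degludec (2 df), at the stated 0.10 level.
- State which p-value, if any, leads to separate analyses. The 3-way term can stay as a description of change over time.
- Report Week 32 treatment differences with 90% CIs in each subgroup whatever the p-value.

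This restores the protocol's treatment-by-factor question at the primary time point and matches the form already used for hypoglycemia rates. It costs a short change to the SAP wording and two CONTRAST/ESTIMATE statements, with no new data and no change to the primary model.
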